10.4.7 Exploratory Efficacy Analyses

Exploratory efficacy analyses will be analyzed on the ITT population using observed data. Imputation will not be applied for any missing data in the exploratory efficacy endpoints.

Analyses will use ANCOVA models with baseline values included as covariates, two-sample t-tests, and Wilcoxon rank sum tests. [REDACTED]

10.4.8 Safety Variables

Adverse events will be coded using the MedDRA dictionary.

Frequencies and percentages of subjects with treatment-emergent adverse events (TEAEs), serious TEAEs, and TEAEs causing premature treatment discontinuation will be provided by treatment group. An AE is treatment emergent if it occurs or worsens after the first dose of study treatment. Furthermore, frequencies will be given of subjects with TEAEs by system organ class and preferred term for the following categories of AEs:

- All TEAEs
- TEAEs at least possibly related to study treatment
- TEAEs leading to study treatment discontinuation
- Serious TEAEs
- By maximal severity
- By study day of onset

Separate analyses will be performed for ocular and non-ocular AEs.

Other safety endpoints will be summarized by treatment group and visit using descriptive statistics. Changes or shifts from baseline will also be summarized where appropriate.

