5 STUDY POPULATION

5.1 Number of Subjects (approximate)

It is estimated that approximately [REDACTED] subjects will be screened to enroll approximately 600 (300 active: 300 placebo) subjects. Subjects will be randomized in a 1:1 ratio to 1.55 µg/mL SkQ1 or placebo.

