9.1.2 Relationship to Investigational Product

The relationship of each adverse event to the Investigational Product (IP) should be determined by the investigator using these explanations:

- *Definite*: When there are good reason and sufficient documentation to demonstrate a direct causal relationship between investigational product and AE;
 - *Probable*: When there are good reasons and sufficient documentation to assume a causal relationship in the sense of plausible, conceivable, likely but not necessarily highly probable.
 - *Possible*: When there is sufficient information to accept the possibility of a causal relationship in the sense of not impossible and not unlikely, although the connection is uncertain or doubtful, for example, due to missing data or insufficient evidence.
- None*: When there is sufficient information to accept a lack of a causal relationship, in the sense of impossible and improbable.

- *Unclassified*: When the causal relationship is not assessable for whatever reason due to insufficient evidence, conflicting data or poor documentation.

Suspected adverse reaction means any adverse event for which there is a reasonable possibility that the IP caused the adverse event. “Reasonable possibility” means there is evidence to suggest a causal relationship between the IP and the adverse event. Types of evidence that would suggest a causal relationship between the IP and the adverse event include: a single occurrence of an event that is uncommon and known to be strongly associated with drug exposure (e.g., angioedema, hepatic injury, Stevens-Johnson Syndrome); one or more occurrences of an event that is not commonly associated with drug exposure, but is otherwise uncommon in the population exposed to the drug (e.g., tendon rupture); an aggregate analysis of specific events observed in a clinical trial (such as known consequences of the underlying disease or condition under investigation or other events that commonly occur in the study population independent of drug therapy) that indicates those events occur more frequently in the drug treatment group than in a concurrent or historical control group.

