10.4.3 Missing Data

The primary efficacy analyses will be performed using Markov Chain Monte Carlo multiple imputation to account for missing Day 57 data. [REDACTED]

In order to show that the primary results are robust to various patterns of missing data, sensitivity models will include the following methods of handling missing data for each primary endpoint:

- Using a control-based pattern mixture for multiple imputation
- Using the last observation carried forward (LOCF) method for missing values
- Analyzing observed data only
- Analyzing observed data for the PP and PPCFS populations for ocular discomfort and conjunctival fluorescein staining, respectively.

Imputation will not be applied for any missing data in the key secondary or exploratory efficacy endpoints.

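### Does the related-TEAE table need a stated rule for events whose causality is rated Unclassified or is missing?

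*Combined protocol and SAP*

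**What the plan says.** Section 10.4.8 (Safety Variables) lists six breakdowns of treatment-emergent events by system organ class and preferred term. One of them is "TEAEs at least possibly related to study treatment"; the synopsis uses the same words. Neither place names the ratings that qualify or mentions Unclassified or missing causality.

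The ratings are in section 9.1.2, where the relationship of each event to the product "should be determined by the investigator using these explanations". Definite and Probable head the list. The other three matter here:

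- **Possible** applies "When there is sufficient information to accept the possibility of a causal relationship", and the definition goes on to allow for doubt: "although the connection is uncertain or doubtful, for example, due to missing data or insufficient evidence".
- **None** applies "When there is sufficient information to accept a lack of a causal relationship, in the sense of impossible and improbable".
- **Unclassified** applies "When the causal relationship is not assessable for whatever reason due to insufficient evidence, conflicting data or poor documentation".

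The missing-data rules in section 10.4.3 concern efficacy only. For example: "Imputation will not be applied for any missing data in the key secondary or exploratory efficacy endpoints".

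**The concern.** A cut that starts at Possible assumes an ordered scale, and Unclassified has no place in that order. A programmer who follows the words keeps Definite, Probable and Possible and drops the rest. An event nobody could assess is then handled like one positively judged unrelated, although section 9.1.2 says that None needs sufficient information and Unclassified reflects a lack of it.

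Insufficient evidence also appears in the definitions of both Possible and Unclassified. Two investigators with the same thin file could choose differently, and only one of the events would enter the table. In a multi-center trial that could make the related count depend partly on site habit. It could also be lower than under a conservative rule that counts everything except None. At stake is the one safety table of the six that rests on causality.

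**Working it through.** There is no figure in the plan to reproduce. The check compares the text and then sizes the effect on stated assumptions.

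**1. Is the cut usable as written?** Applied to the five ratings in 9.1.2, a threshold at Possible selects Possible, Probable and Definite. No other selection fits the words. What is absent is a confirmation of that reading.

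**2. Are Possible and Unclassified interchangeable?** The entry conditions differ. Possible requires enough information to accept that a causal link may exist; thin evidence is then an example of why the accepted possibility remains doubtful. Unclassified requires that no assessment can be made; thin evidence is one reason for that. The shared phrase leaves a margin for judgement, but the ratings are distinct.

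**3. What about missing causality?** Section 9.1 asks for relationship to the product to be documented for an adverse event. Section 9.1.2 asks for a determination on each event. Section 8.3.1 has the investigator promptly review adverse events for accuracy and completeness. An event that cannot be assessed for any reason already has a rating, Unclassified. True blanks should therefore be few.

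**4. Does section 9.1.2 require the conservative rule?** It ties a suspected adverse reaction to a reasonable possibility, explained as evidence suggesting a causal link. A non-assessable event does not plainly meet that. Counting it under a label that says at least possibly related would mix assessed with unassessed events.

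**5. How large could the difference be?**

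- *n* = 300 per arm (section 5.1: "enroll approximately 600 (300 active: 300 placebo) subjects"). The safety population may be slightly smaller.
- *u* = subjects in an arm whose only candidate event is Unclassified or missing. The documents give no value, so *u* = 0, 1, 3 and 6 are assumptions.
- Shift in that arm's related rate = *u*/*n*.

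| *u* | Shift in the arm's rate |
|---|---|
| 0 | 0 |
| 1 | 1/300 = 0.33 points |
| 3 | 3/300 = 1.0 point |
| 6 | 6/300 = 2.0 points |

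The shift in the difference between arms is (*u* active − *u* placebo)/300. With three such subjects in each arm it is (3 − 3)/300 = 0; with six against none it is 6/300 = 2.0 points. Masked rating gives no reason to expect the second pattern in a particular direction.

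Relative changes are less informative. If 5% of an arm had a related event (300 × 0.05 = 15 subjects), adding 1% or 5% (3 or 15 subjects) gives 18 or 30, an increase of 20% or 100%. At 10% related (30 subjects) the same additions give 33 or 45, an increase of 10% or 50%. All these rates are assumed, so the percentages only return what was put in.

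**6. What uses the table?** It holds frequencies. No hypothesis in section 10.2 refers to it, and section 10.4.9 rules out interim analyses. Every treatment-emergent event left out of it remains in All TEAEs and in the severity and onset-day breakdowns, and in the serious and discontinuation breakdowns where they apply.

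**The case for a change.** The best case for a change is that it costs almost nothing. One sentence in two places and one extra row would fix the rule before unmasking, remove a post-hoc choice, and let a reader see the related count both ways. System organ class and preferred term cells, split again into ocular and non-ocular events, may be small, so one or two events could be noticeable. Leaving unassessed events on the unrelated side is also the less cautious default.

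Much of this stands. The rule is not spelled out, no redaction mark in the relevant lists explains the gap, and a separate row would be good practice. It does not amount to a defect in the plan, for three reasons. The literal wording already fixes a default before unmasking, so there is little room for a later choice. Counting Unclassified as related would not end the dependence on rating habits; it would move the deciding margin to Unclassified versus None. And the comparison that randomization protects is All TEAEs by arm, which needs no causality rating. Section 9.1.2 itself cites aggregate comparison with a control group as evidence of causation.

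**Conclusion.** No change to the plan is needed. The text is silent on Unclassified and missing causality, but the gap is one that analysts fill sensibly in the table shells: name the three ratings counted and report Unclassified separately if any occur. Counting such events as related is a defensible convention that the protocol's definitions do not require.

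The size cannot be derived from the documents. It is 0.33 percentage points in an arm's related rate per affected subject, or 0 to 2.0 points for an assumed 0 to 6 subjects among 300. No efficacy test, error rate or power figure is touched, and no between-arm bias is shown. The conclusion rests on the natural reading of the threshold, on causality being collected as sections 9.1 and 9.1.2 direct, and on All TEAEs being reported as planned. If Unclassified were used often, the All TEAEs comparison would still be complete; only the related table would need reading with care.

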10.4.9 Interim Analyses

There will be no interim analyses.

11 COMPLIANCE WITH GOOD CLINICAL PRACTICES, ETHICAL CONSIDERATIONS, AND ADMINISTRATIVE ISSUES

This study will be conducted in compliance with the protocol, Good Clinical Practices (GCPs), including the International Conference on Harmonization (ICH) Guidelines, and in general, consistent with the Declaration of Helsinki. In addition, all applicable local, state, and federal requirements relevant to the use of study drugs in the countries involved will be adhered to.

11.1 Protection of Human Subjects

11.1.1 Subject Informed Consent

Informed consent/assent must take place before any study specific procedures are initiated. Signed and dated written informed consent must be obtained from each subject prior to enrollment into the study.

All informed consent forms must be approved for use by the sponsor and receive approval/favorable opinion from an IRB prior to their use. If the consent form requires revision (e.g., due to a protocol amendment or significant new safety information), it is the investigator's responsibility to ensure that the amended informed consent is reviewed and approved by Ora prior to submission to the governing IRB and that it is read, signed and dated by all subjects subsequently enrolled in the study as well as those currently enrolled in the study.

11.1.2 Institutional Review Board (IRB) Approval

This study is to be conducted in accordance with Institutional Review Board regulations (U.S. 21 CFR Part 56.103). The investigator must obtain appropriate IRB approval before initiating the study and re-approval at least annually.

Only an IRB approved version of the informed consent form will be used.

11.2 Ethical Conduct of the Study

This study will be conducted in accordance with the ethical principles that originated with the Declaration of Helsinki.

11.3 Subject Confidentiality

All personal study subject data collected and processed for the purposes of this study should be maintained by the investigator and his/her staff with adequate precautions as to ensure that the confidentiality of the data in accordance with local, state, and federal laws and regulations.

Monitors, auditors and other authorized representatives of Ora, the sponsor, the IRB approving this study, the FDA, the DHHS, other domestic government agencies, and other foreign regulatory agencies will be granted direct access to the study subject's original medical and study records for verification of the data and/or clinical trial procedures. Access to this information will be permitted to the aforementioned individuals to the extent permitted by law.

A report of the results of this study may be published or sent to the appropriate health authorities in any country in which the study drug may ultimately be marketed, but the subject's identity will not be disclosed in these documents.

11.4 Documentation

Source documents may include a subject's medical records, hospital charts, clinic charts, the investigator's study subject files, as well as the results of diagnostic tests such as X-rays, laboratory tests, and EKGs. The investigator's copy of the eCRF serves as the investigator's record of a subject's study-related data.

11.4.1 Retention of Documentation

All study-related source documents, correspondence, patient records, consent forms, record of the distribution and use of all study drug and copies of case report forms should be maintained on file for at least two years after the last approval of a marketing application in an ICH region and until there are no pending or contemplated marketing applications in an ICH region; or until at least two years have elapsed since the formal discontinuation of clinical development of the study drug. These documents will be retained for a longer period if required by the applicable regulatory requirements or by an agreement with the sponsor. It is the responsibility of the sponsor to inform the investigator/institution as to when these documents no longer need to be retained.

If the responsible investigator retires, relocates, or for other reasons withdraws from the responsibility of keeping study records, custody must be transferred to a person who will accept the responsibility. The sponsor must be notified in writing of the name and address of the new custodian.

11.5 Labeling, Packaging, Storage, Accountability, and Return or Disposal of Study Drug

11.5.1 Labeling/Packaging

All run-in and study drug will be labeled according to applicable regulatory requirements.

11.5.2 Storage of Study Drug

11.5.3 Accountability of Study Drug

The study drug is to only be prescribed by the principal investigator or his/her named sub investigator(s), and is to only be used in accordance with this protocol. The study drug must only be distributed to subjects properly qualified under this protocol to receive study drug. The investigator must keep an accurate accounting of the study drug by maintaining a detailed inventory. This includes the amount of study drug received by the site, amount dispensed to subjects, amount returned to the site by the subjects, and the amount returned to the Sponsor upon the completion of the study.

11.5.4 Return or Disposal of Study Drug

All study drug will be returned to the sponsor or their designee or destroyed on behalf of the Sponsor following local regulations.

11.6 Recording of Data on Source Documents and electronic Case Reports Forms (eCRFs)

The investigator is responsible for ensuring that study data is completely and accurately recorded on each subject's eCRF, source document, and all study-related material. All study data should also be attributable, legible, contemporaneous, and original. Recorded datum should only be corrected in a manner that does not obliterate, destroy, or render illegible the previous entry (e.g., by drawing a single line through the incorrect entry and writing the revision next to the corrected data). An individual who has corrected a data

entry should make clear who made the correction and when, by adding to the correction his/her initials as well as the date of the correction.

11.7 Publications

Authorship and manuscript composition will reflect cooperation among all parties involved in the study. Authorship will be established before writing the manuscript. Ora and the study sponsor will have the final decision regarding the manuscript and publication.

